5. STUDY DESIGN

5.1. Overall Design

This is a Phase IIb, multicenter, randomized, stratified, double-blind (Sponsor Open), placebo-controlled, parallel-group study in participants who present with an acute moderate or severe exacerbation of COPD requiring SoC.

Standard of Care (SoC) for the index exacerbation is defined for this protocol as treatment with oral/systemic corticosteroid[s] (prednisone 40 mg/day or equivalent) for 5 days **and** antibiotic[s] for 7 days; the dose and/or duration of prednisone (40 mg/day or equivalent) and/or the antibiotic can be modified according to the Investigator's/medically qualified designee's judgement or according to local country/institution practice. The start of SoC is defined as the start of either oral/systemic corticosteroids[s] or antibiotic[s] whichever is earliest.

In addition to double-blind study treatment and SoC treatment for the COPD exacerbation, other treatment(s) for the exacerbation (i.e., bronchodilators) and regular COPD maintenance therapy are permitted.

Participants will be randomised in a ratio of 3:1:1:1:1:3 to receive placebo, or nemoralisib doses of 12.5 mcg, 50 mcg, 100 mcg, 250 mcg, 500 mcg or 750 mcg. The option to add a dose strength of 25 mcg following the results of an unblinded interim analysis has been included if further characterization of the lower end of the dose response curve is required.

Patients will be stratified according to their index exacerbation: moderate or severe, and whether or not they are in the PK substudy. The definition of moderate and severe exacerbations is given in [Appendix 9](#):

This study consists of a Screening Period, a 12-Week Treatment Period and a 12-Week Post-Treatment Follow-Up Period. Participants will visit the hospital /clinic a minimum of eight to nine times over a 24-week period as shown in [Figure 1](#). Randomization and the first dose of the double-blind study treatment administration (Visit 2/Day 1) should take place in the morning, as soon as possible following determination of eligibility and completion of the baseline PRO measures, including the EXACT-PRO questionnaire for the day of randomization, and FEV₁ measurement and no later than 48hrs after the start of SoC.

Note: In the event that completion of the assessments/procedures at Visit 2 (or in cases where Visit 1 and Visit 2 are conducted on the same day) extends past noon, the first dose of the double-blind study treatment administration may occur up until 3:00 pm on Day 1. After Day 1, dosing should take place in the morning each day through the end of the 12-Week Double-Blind Treatment Period

[figure not shown]
For participants who are hospitalized:

1. If discharge takes place before day 11, participants must then visit the unit/clinic on Day 14 (\pm 3 day) (Visit 3) for assessments.
2. If discharge takes place between Day 11 and Day 17 (inclusive), the assessments planned for Day 14 (Visit 3) may be completed on the day of discharge.

On the day of discharge, FEV₁ measurements should be performed in the morning prior to discharge, including pre-bronchodilator measurements and post-bronchodilator measurements.

The total duration of study participation is approximately 170 days.

Figure 1 Study Schematic

Clinic Visit:	1	2 ⁵	3	4	5	6 ⁶	7	8	9 ⁷
Day:	-2 to -1	1	14 (±3)	28 (±3)	56 (-4/+3)	84(-4/+3)	112 (-4/+3)	140 (-4/+3)	168 (-4/+3)

QD=once daily; SoC=Standard of Care

1. Inhalation Powder administered once-daily in the morning via the ELLIPTA inhaler
2. For this study, SoC for the index exacerbation is defined for this protocol as treatment of the COPD exacerbation with oral/systemic corticosteroid[s] (prednisone 40 mg/day or equivalent) for 5 days **and** antibiotic[s] for 7 days; the dose and/or duration of prednisone (or equivalent) and/or the antibiotic can be modified according to local country/institution practice. The start of SoC is defined as the start of either oral/systemic corticosteroids[s] or antibiotic[s] whichever is earliest
3. Note: subjects may receive additional treatment[s] for the exacerbation (e.g., bronchodilator) and will be on a background of regular COPD maintenance therapy
4. These figures are approximate and assume that no further adjustments to the randomization ratio are made. The actual sample sizes at the end of the study may be different, depending upon whether changes are made following the results of the unblinded interim analysis which may modify the planned allocation
5. Randomization and first dose of double-blind (Sponsor Open) study treatment
6. End of Treatment Period (last dose of double-blind [Sponsor Open] study treatment)
7. Last day of study
8. The option to add a dose strength of 25 mcg following the results of an unblinded interim analysis has been included if further characterization of the lower end of the dose response curve is required

PK Subgroup: Sparse PK sampling will be conducted at selected sites. The PK Subgroup will be identical to the main study in terms of the study population, design, and conduct, with the exception of blood draws (3 per visit on Days 14 and 28) for PK analysis.

An internal Safety Review Committee (iSRC) will have study oversight to ensure that it meets the highest standards of ethics and participant safety and to carry out the planned

interim safety data analyses/data reviews. Data will be reviewed by the iSRC on a periodic basis, as defined in the iSRC Charter. The iSRC, which will comprise a minimum of 3 people (including an independent statistician, and an independent clinician with experience in respiratory and general medicine), will be authorized to review unblinded interim safety analyses/data during the study; see Section 10.3.5.

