1. The start of the SoC for the index exacerbation is defined as the start of either oral/systemic corticosteroids[s] or antibiotic[s] whichever is earliest and is expected to start shortly after diagnosis, though it may already have been started before formal diagnosis of COPD exacerbation. If SoC is started >48 hours prior to diagnosis, the participant is not eligible to participate, but may be re-screened in the future as described in the main protocol.
2. All Screening/baseline assessments should be completed within 48hrs of start of SoC.

12-Week Double-Blind Treatment Period: Once-daily study treatment administration will start on Day 1 (Visit 2).

At the end of the Screening Period (-2 to -1/0 days), participants who meet all of the Inclusion Criteria and none of the Exclusion Criteria will complete Visit 2 (Randomization Visit/Day 1). If a participant meets all of the eligibility criteria, it is possible for him/her to complete the Screening Visit and the Randomization Visit on the same day (e.g., outpatient participant who presents with an acute moderate exacerbation of COPD).

At this visit, participants will be randomized to receive one of the doses of nemoralisib QD or placebo QD in addition to SoC for 12 weeks.

Randomization and the first dose of the double-blind study treatment administration should take place in the morning, as soon as possible following determination of eligibility and completion of the baseline PRO measures, including the EXACT-PRO questionnaire for the day of randomization, and FEV₁ measurement and no later than 48hrs after the start of SoC.

Note: In the event that completion of the assessments/procedures at Visit 2 (or in cases where Visit 1 and Visit 2 are conducted on the same day) extends past noon, the first dose of the double-blind study treatment administration may occur up until 3:00 pm on Day 1. After Day 1, dosing should take place in the morning each day through the end of the 12-Week Double-Blind Treatment Period.

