6. For participants hospitalized for the index exacerbation at Screening, spirometry (as noted in the bullet above) should also be performed in the morning on the day of discharge
7. Pre-dose
8. Single assessment

9. Screening: Due to the short screening window, local laboratory results will be used for purposes of determining subject eligibility for randomization. If local laboratory results are already available within 48 hours from diagnosis of the index COPD exacerbation, these results can be used for determination of subject eligibility; there is no need to take another sample for local analysis. A sample for central laboratory analysis should also be obtained.
10. Presence of hepatitis B surface antigen (HBsAg) and/or positive hepatitis C antibody test result at Screening or within 3 months prior to first dose of study treatment or positive test for HIV antibody is exclusionary. NOTE: Participants with positive Hepatitis C antibody due to prior resolved disease can be enrolled, only if a confirmatory negative Hepatitis C RNA test is obtained. Positive hepatitis C RNA test result at Screening or within 3 months prior to first dose of study treatment is exclusionary. NOTE: Hepatitis C RNA test is optional and participants with negative Hepatitis C antibody test are not required to also undergo Hepatitis C RNA testing. Because of the short window for Screening, double-blind study treatment may start before the results of the hepatitis and HIV tests have been received. If subsequently the test(s) is(are) found to be positive, the participant will need to be withdrawn from study treatment and may also be withdrawn from the study as judged by the Principal Investigator in consultation with the Medical Monitor.
11. If the urine pregnancy text result is positive, a blood sample for serum pregnancy testing will need to be conducted to confirm pregnancy status
12. Approximately 20 mL (4 teaspoons) of blood will be collected in all participants at each time point noted; at Screening, the sample should be collected as soon as possible after the participant has completed the informed consent and PRO assessments
13. Informed consent for optional sub-studies (e.g. genetics research, PK) must be obtained before collecting a sample/performing procedure
14. Collected at Visit 2 or any time post-randomization if unable to collect at Visit 2

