Spirometry assessments performed during a moderate or severe COPD exacerbation.		If a participant is unable to achieve the required standard of spirometry per Section 9.1.1 during a moderate or severe COPD exacerbation, they will be permitted to continue in the study. The protocol has anticipated that this is likely for hospitalised participants and therefore spirometry will be repeated at discharge for a secondary endpoint.
Feeling faint, or experiencing mild pain, bruising, irritation or redness at the injection site during the blood withdrawals In rare cases, an infection where the needle entered the skin		The medically qualified site staff conducting the phlebotomy will follow standard medical practice to minimize these risks
Skin irritation from the ECG electrodes placed on the participant's chest		The medically qualified site staff conducting the ECG measurement will follow standard medical practice for performing the ECG
Risk of radiation from a chest X-ray		As specified in the protocol: 
 • A chest X-ray (CT scan), for purposes of determining participant eligibility, will be performed only at the Screening (Visit 1).

Potential Risk of Clinical Significance	Summary of Data/Rationale for Risk	Mitigation Strategy
		

• A chest X-ray (conducted within 48 hours of diagnosis) for confirmation of a suspected case of pneumonia, is encouraged rather than required

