4. OBJECTIVES AND ENDPOINTS

Objectives	Endpoints

Primary
 
 To characterize the dose response of nemiralisib administered in addition to SoC compared with placebo and SoC in participants diagnosed with an acute moderate or severe exacerbation of COPD 	
 Change from baseline in Clinic Visit trough forced expiratory volume in one second (FEV₁) at Day 84 measured post-bronchodilator Baseline is defined as the post-bronchodilator FEV₁ measured prior to the first dose of double-blind study treatment on Day 1.

Secondary
 
 To characterize the dose response and efficacy of nemiralisib administered in addition to SoC compared with placebo and SoC in participants diagnosed with an acute moderate or severe exacerbation of COPD 	
 Rate of moderate and severe exacerbations over the 12-Week Treatment Period Time to next moderate/severe exacerbation following index exacerbation Change from baseline in Clinic Visit trough FEV₁ measured pre and post-bronchodilator at Days 14, 28, 56, and 84 (Day 84: post-bronchodilator is the primary endpoint; pre-bronchodilator is a secondary endpoint) and at hospital discharge (only for participants who are hospitalized for the index

Objectives	Endpoints

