
 To evaluate the treatment effect of nemiralisib in addition to SoC compared with placebo and SoC on symptoms indicative of an exacerbation and on health status using Patient-Reported Outcomes (PROs) in participants diagnosed with an acute moderate or severe exacerbation of COPD To evaluate the usage of rescue medication in participants diagnosed with an acute moderate or severe exacerbation of COPD 	
exacerbation)
 
 Change from hospital discharge in clinic visit trough FEV₁ measured pre- and post-bronchodilator at Days, 14, 28, 56, and 84 (in participants hospitalized for index exacerbation only) 
EXAcerbations of Chronic Pulmonary Disease Tool (EXACT-PRO)
 
 Proportion of participants achieving the EXACT definition of recovery from the index exacerbation by Days 14, 28, 56, and 84 Time to recovery from index exacerbation Severity of subsequent HCRU-defined exacerbation(s) defined by EXACT 
COPD Assessment Test (CAT)
 
 Proportion of responders using the CAT at Treatment Days 28, 56, and 84, and following EXACT defined recovery from the index exacerbation Change from baseline (Day 1) in CAT total score at Days 28, 56, and 84 and following EXACT defined recovery from the index exacerbation 
St. George's Respiratory Questionnaire (SGRQ) Total Score
 
 Proportion of responders on the SGRQ total score as measured by the SGRQ for COPD Patients (SGRQ-C) at Days 28, 56, and 84 Change from baseline (Day 1) in SGRQ total score at Days 28, 56, and 84 Rescue medication use (occasions/day), averaged over each week of treatment and over the 84-day treatment period The percentage of rescue-free days (24-

Objectives	Endpoints

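### In hospitalised participants, the change-from-discharge FEV1 endpoint uses a reference normally taken after dosing has begun, and at Day 14 it can compare a session with itself

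*Protocol*

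**What the plan says.** The Protocol's Synopsis and Section 4 list as a secondary endpoint "Change from hospital discharge in clinic visit trough FEV₁ measured pre- and post-bronchodilator at Days, 14, 28, 56, and 84", restricted to those "in participants hospitalized for index exacerbation only". It sits under the secondary objective on dose response and efficacy, which is framed as a comparison with placebo plus SoC.

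The primary endpoint uses a different reference: post-bronchodilator FEV1 "measured prior to the first dose of double-blind study treatment on Day 1". Section 5.1 puts randomisation and first dose no later than 48 hours after the start of SoC.

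The Schedule of Activities (footnote 6) adds a session for those hospitalised at Screening: "spirometry (as noted in the bullet above) should also be performed in the morning on the day of discharge". Section 3.3.1 gives the background. Hospitalised participants may not meet the spirometry standard during the exacerbation, and "therefore spirometry will be repeated at discharge for a secondary endpoint". The same secondary list also has change from baseline at hospital discharge, so discharge FEV1 appears there as an outcome.

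Section 5.1 sets two rules for hospitalised participants. If discharge is before Day 11, a separate Visit 3 follows on Day 14 (±3 days). If discharge falls on Days 11 to 17 inclusive, "the assessments planned for Day 14 (Visit 3) may be completed on the day of discharge". There is no rule for discharge after Day 17.

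**The concern.** A reference value for comparing randomised arms should be fixed before treatment can influence it. Discharge FEV1 normally is not. The participant has been randomised and dosed by then, and the protocol elsewhere counts that measurement as an outcome. The date of discharge may also depend on how quickly the participant recovers, so both the value and the timing of the reference are open to influence by treatment.

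Two consequences follow. At every listed day, the between-arm difference reflects only what is gained after discharge. At Day 14, the reference and the follow-up value can be one session, or can fall in the wrong order. A reader who takes this endpoint as a measure of the drug's effect in hospitalised participants would understate any benefit that arrives early.

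**Working it through.** The protocol states no sample size, power or effect for this endpoint, so there is no figure to reproduce. The check is algebraic, with illustrative numbers from Section 10.1.1.

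**Effect removed by the reference.** Let e(t) be the mean difference from placebo in FEV1 at time t.

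- Change from the pre-dose Day 1 baseline: the expected contrast is e(t).
- Change from discharge: the expected contrast is e(t) − e(discharge).

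Inputs are the 750 mcg and placebo values in Table 3, which describe change from baseline:

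- Scenario 1: 80 − (−20) = 100 mL
- Scenario 2: 50 − (−20) = 70 mL
- Scenario 3: 0 − (−20) = 20 mL

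If a fraction f of the effect is present at discharge, the contrast is e × (1 − f). The protocol does not give f, so a range is shown.

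| f (assumed) | Scenario 1 | Scenario 2 | Scenario 3 |
|---|---|---|---|
| 0 | 100 mL | 70 mL | 20 mL |
| 0.25 | 75 mL | 52.5 mL | 15 mL |
| 0.50 | 50 mL | 35 mL | 10 mL |
| 0.75 | 25 mL | 17.5 mL | 5 mL |
| 1 | 0 mL | 0 mL | 0 mL |

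**Day 14 when the visits are combined.** Discharge spirometry and Visit 3 spirometry are the same procedure: a morning session, before and after bronchodilator. Section 5.1 asks for no second session when the visits are combined, and the endpoint does not exclude that case. Day 14 value minus discharge value is then x − x = 0 for each such participant in every arm.

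If a share s of hospitalised participants uses the option, the Day 14 contrast becomes (1 − s) × [e(14) − e(discharge)]. The protocol does not give s. Assume for illustration that e(14) = 100 mL and that half the effect is present at discharge, so the bracket is 50 mL.

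The exact zeros also shrink the spread. With the Section 10.1.1 values (SD 300 mL, correlation 0.7), applied here by assumption to the discharge and Day 14 pair, the SD of change is 300 × √(2 × (1 − 0.7)) = 232 mL. In an arm with mean change 0 this falls to 232 × √(1 − s).

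| s (assumed) | Day 14 contrast | SD of change |
|---|---|---|
| 0 | 50 mL | 232 mL |
| 0.10 | 45 mL | 220 mL |
| 0.25 | 37.5 mL | 201 mL |
| 0.50 | 25 mL | 164 mL |
| 1 | 0 mL | 0 mL |

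A simulation on the same assumptions gave contrasts of 51.1, 43.8, 37.7, 25.0 and 0.0 mL, in agreement.

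**Order of the sessions.**

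| Discharge | Day 14 session relative to discharge session |
|---|---|
| Before Day 11 | Separate and later, as intended |
| Days 11–17, option used | The same session; change is 0 |
| Days 11–17, Visit 3 already done | Earlier than its own reference |
| After Day 17, Visit 3 done in its window | Earlier than its own reference; no rule given |

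**The case against.** The strongest reply is that little depends on this endpoint. The primary endpoint, the key secondary endpoint and the stated success criteria do not use it. The same list already has change from the pre-dose Day 1 baseline at the same days and at discharge, so anyone with usable Visit 2 spirometry has a sound comparison. All of that stands, and it limits the weight of the point.

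A second reply is that Section 10.3.1 gives methods only for the primary and key secondary endpoints, and that handling a coinciding visit is a derivation rule for the analysis plan. It is true that no test or model is specified here. But the protocol itself fixes the reference, the list of days including Day 14, and the shared-visit option, and it places the endpoint under an objective framed against placebo. An analysis plan that follows the text inherits the problem.

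Several stronger readings are tempting, and the documents do not support them:

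- **The whole drug effect is subtracted.** Only the part accrued by discharge is removed. A discharge on Day 1 before the first dose would even give a pre-dose reference.
- **The Day 14 change is zero for everyone.** This needs discharge on Days 11 to 17 and use of an optional rule. The documents give no length of stay, so the affected share is unknown and may be small.
- **The endpoint would show a reversed effect.** That requires the effect at discharge to exceed the later effect. The table above, with f from 0 to 1, never falls below 0 mL.
- **The endpoint is the declared replacement for a missing baseline.** Section 3.3.1 says only that discharge spirometry serves a secondary endpoint, and two secondary endpoints use it.
- **The severe stratum is affected as a whole.** The endpoint covers participants hospitalised for the index event. Appendix 9 also classes emergency-room visits as severe.

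**Conclusion.** The point holds in a limited form. A between-arm comparison of change from discharge measures e(t) − e(discharge), not the effect from the start of treatment. Under Scenario 1 the loss is 100 × f mL, and under Scenarios 2 and 3 it is 70 × f and 20 × f mL. The fraction f is an assumption throughout.

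At Day 14 the change is exactly 0 in every arm for participants whose Visit 3 is completed on the day of discharge, and it runs backwards in time when discharge follows Visit 3. These two results follow from the text and need no numerical assumption. How many participants they affect cannot be derived from the protocol.

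This is a defect in one non-key secondary endpoint in the hospitalised subset, worth correcting because the correction is cheap. It does not threaten the trial's main conclusions.

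**What to change.** Amend the endpoint wording in the Synopsis and Section 4:

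1. Base treatment comparisons in hospitalised participants on the pre-dose Visit 2 baseline, using the existing change-from-baseline endpoint at Days 14, 28, 56 and 84 and at discharge.
2. Keep change from discharge as a within-arm description of the post-discharge course.
3. Compute it only at scheduled visits after the discharge session. Omit Day 14 when Visit 3 coincides with or precedes that session, which also covers discharge after Day 17.

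No assessment is added. The cost is a wording change, and one non-key secondary between-arm comparison becomes descriptive. Participants without usable Visit 2 spirometry would still lack a change from baseline. A between-arm analysis of their observed FEV1 would be a new comparison with its own cost, and it is not part of this change.

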5.2. Number of Participants

Approximately 1,667 participants will be screened (assumes an approximate 25% Screen Failure rate) to achieve approximately 1,250 randomized participants (assumes an approximate 20% withdrawal rate) such that approximately 1,000 participants complete the 12-week Treatment Period. Randomization will be stratified by index COPD exacerbation severity (moderate or severe) and by whether or not that participant is in the PK Subgroup, to ensure a balance across treatments within each strata.

The plan is to randomize approximately 340 participants each to the placebo and nemiralisib 750 mcg groups and approximately 570 participants across the other nemiralisib groups. The reason for inflating the sample size for a selected dose of nemiralisib (planned as the 750 mcg dose) and the placebo group is for the aim to increase precision around the pair-wise comparison between them for the key secondary objective of the reduction in the rate of re-exacerbations.

See Section 10.1 Sample Size Determination for additional details, including how screening failures and non-evaluable participants are defined.

